7.5 Follow-Up Visit Day 141 (Week 20) (+/- 7 Days)

- Measure vital signs.
- Collect concomitant medication and procedure/therapy information.
- Review and record AEs.
- Complete the following assessments:
 - Investigator’s Global Assessment (IGA)
 - Eczema Area and Severity Index (EASI)
- Remind the patient to apply an emollient twice daily
- Schedule next visit.

7.6 Follow-Up Visit Day 169 (Week 24) (+/- 7 Days)

- Measure vital signs.
- Collect concomitant medication and procedure/therapy information.
- Review and record AEs.
- Draw blood samples for laboratory tests (hematology and chemistry)
- Draw blood sample for PK and ADA testing.
- Collect urine for urinalysis and urine pregnancy test (WOCBP only).
- Complete the following assessments:
 - Investigator’s Global Assessment (IGA)
 - Body Surface Area (BSA).
 - Eczema Area and Severity Index (EASI)

- Remind the patient to apply an emollient twice daily
- Add reminder to schedule a FU visit phone call.

7.7 Follow-Up Visit Phone Call, Day 225 (Week 32) (+/- 7 Days)

- Review and record AEs.

7.8 Unscheduled Visits

If an unscheduled visit is necessary, the following assessments should be included in the visit along with any assessments that are the reason for the visit (e.g., blood draw for a repeat of abnormal lab values):

- Measure vital signs.
- Collect concomitant medication and procedure/therapy information.
- Review and record AEs.

8 DETAILS OF ASSESSMENTS

8.1 Screening Assessments

8.1.1 Demographics

At the screening visit, demographic information including age, gender, race and ethnicity will be collected and recorded in the eCRF for each patient.

8.1.2 Medical History

A complete medical history will be collected as part of the screening assessment and include all clinically relevant past or coexisting medical conditions or surgeries. Extensive information on the patient's atopic dermatitis, asthma, and allergies will be collected as part of the medical history. The medical history will be updated prior to treatment on Baseline/Day 1 should new findings be present since the screening visit. Findings will be recorded in the eCRF.

8.1.3 Disease Specific Information

Information on the patient's atopic dermatitis will be collected as part of the screening assessment and include the date of onset of atopic dermatitis, anatomical areas affected by atopic dermatitis, and past treatments for atopic dermatitis. Information will be recorded in the eCRF.

8.2 Assessment of Efficacy

8.2.1 AD Assessments

Each patient's AD will be assessed as specified in the Schedule of Visits and Procedures. Whenever possible, the same assessor should perform all assessments on a given patient. Individuals will be trained and certified by the Sponsor prior to conducting any assessments.

8.2.1.1 Investigator Global Assessment (IGA)

The IGA ([Appendix 3](#)) is an instrument used to globally rate the severity of the patient's AD and is based on a 5-point scale ranging from 0 (clear) to 4 (severe). The IGA must be conducted prior to conducting the EASI assessment.

A grade of 0 to 4 will be assessed by the Investigator or designee. Assessors must be trained and certified by the Sponsor prior to conducting this assessment. Assessments will be recorded in the eCRF.

8.2.1.2 Eczema Area and Severity Index (EASI)

The EASI ([Appendix 4](#)) is used to assess the severity and extent of AD; it is a composite index with scores ranging from 0 to 72, with the higher values indicating more severe and or extensive disease. A grade of 0 to 72 will be assessed by the Investigator or designee.

Assessors must be trained and certified by the Sponsor prior to conducting this assessment. Assessments will be recorded in the eCRF.

8.2.1.3 Body Surface Area (BSA)

The BSA ([Appendix 5](#)) assessment estimates the extent of disease or skin involvement with respect to AD and is expressed as a percentage of total body surface. BSA will be determined by the Investigator or designee using the patient palm = 1% rule.

Assessments will be recorded in the eCRF. Assessors must be trained and certified by the Sponsor prior to conducting this assessment.

8.2.1.4 Pruritus

Pruritus will be assessed by the patient using a Pruritus Numeric Rating Scale (NRS) ([Appendix 6](#)). The Pruritus NRS is an 11-point scale used by patients to assess their worst itch severity over the past 24 hours with 0 indicating “No itch” and 10 indicating “Worst itch imaginable”. At Week 16, a global impression of change for itching question will be requested.

Assessments will be recorded daily by the patient using an electronic diary and transferred into the clinical database.

8.2.1.5 Sleep-Loss

Quality of sleep will be assessed by the patient using a sleep-loss question ([Appendix 7](#)) over the past 24 hours.

Assessments will be recorded daily by the patient using an electronic diary and transferred into the clinical database.

8.2.1.6 Atopic Dermatitis Impact Questionnaire (ADIQ)

The ADIQ ([Appendix 8](#)) is a 17-item questionnaire used to assess the patients’ AD-specific health-related QoL. The questionnaire assesses AD’s impact on emotions, energy, activities of daily living, and social activities. The ADIQ has a recall specification of 7 days.

Assessments will be recorded by the patient using an electronic diary and transferred into the clinical database.

8.2.1.7 Patient Oriented Eczema Measure (POEM)

The POEM ([Appendix 9](#)) is a 7-item questionnaire used by the patient to assess the severity of the patient’s eczema over the last week. All seven answers carry equal weight and are scored as: No days=0; 1– 2 days =1; 3–4 days=2; 5–6 days=3; everyday=4.

The POEM is completed by the patient in the clinic. Assessments will be recorded in the eCRF.

8.2.1.8 Dermatology Life Quality Index (DLQI)

The DLQI ([Appendix 10](#)) is a 10-question instrument used to measure the impact of skin disease on the quality of life of an affected person. The 10 questions cover the following topics: symptoms, embarrassment, shopping and home care, clothes, social and leisure, sport, work or study, close relationships, sex, and treatment, over the previous week.

Questions are scored from 0 to 3, giving a possible total score range from 0 (meaning no impact of skin disease on quality of life) to 30 (meaning maximum impact on quality of life).

The DLQI is completed by the patient in the study clinic. Assessments will be recorded in the eCRF.

8.2.1.9 Hospital Anxiety and Depression Scale (HADS)

The HADS ([Appendix 11](#)) assesses anxiety and depression in a non-psychiatric population. The HADS has two subscales (depression and anxiety), both with 7 questions.

Responses are based on the relative frequency of symptoms over the past week, using a four-point scale ranging from 0 (not at all) to 3 (very often indeed).

HADS is completed by the patient in the clinic. Assessments will be recorded in the eCRF.

8.2.1.10 Global Assessment of Change–AD

The Global Assessment of Change for AD ([Appendix 12](#)) will be one question asked at Week 16 and the Early-Termination visit. The value of the question is to capture the patient's impression of overall change in their AD.

This will be completed by the patient in the clinic. Assessments will be recorded in the eCRF

8.2.2 PK and ADA Sampling

Serum PK and ADA samples on Day 1, 15, 29, 57 (PK only), 85 (PK only), 113, and 169 will be taken predose. PK and ADA samples will be collected from all patients including those assigned to the placebo group to maintain the blinding of the treatment assignment. Positive ADA results will be further evaluated for antidrug antibodies. The procedural instructions will be provided in a separate PK and Serum Antibody Sampling manual.

9 ASSESSMENT OF SAFETY

9.1 Assessment of Safety

9.1.1 Physical Examination

A complete physical examination will be conducted at screening and cover general appearance, dermatological, head, ears, eyes, nose, throat, respiratory, cardiovascular, abdominal, neurological, musculoskeletal, and lymphatic body systems. Height and weight will be recorded as part of the screening physical exam and only the patient's weight will be recorded with the Baseline and the week 16 physical examination. Findings will be recorded in the eCRF.

At subsequent study visits, a symptom-directed physical examination may be conducted.

9.1.2 Vital Signs

Vital signs, including body temperature, respiratory rate (breath per minute), pulse (beats per minute), and blood pressure (mmHg), will be obtained with the patient in the seated position,

after sitting for at least 5 minutes. Any abnormal findings which are new or worsened in severity and clinically significant, in the opinion of the Investigator, will be recorded as an AE. Vital sign measurements will be recorded in the eCRF.

9.1.3 ECGs

12-lead ECG measurements will be obtained in all patients. The patient should rest quietly for at least 5 minutes in a supine position prior to ECG collection. The ECG should be obtained either prior to the time of blood collection, or at least 15 minutes afterwards. The medical monitor may be consulted if needed for interpretation of ECGs.

All study sites will be supplied with standardized, validated, digital, 12-lead ECG machine (12-lead at 25 mm/sec reporting rhythm, ventricular rate, the RR interval, the PR interval, QRS duration, QT and QTcF intervals) capable of recording, storing, printing, and producing high resolution 12-lead ECG data. Study sites will be trained on the use of the equipment prior to study start.

Machine-read ECG recordings will be collected and analyzed centrally. Data will be transferred electronically to the database.

9.1.4 Laboratory Evaluations

Laboratory tests will be analyzed using a central laboratory and include hematology with differential, serology, a standard chemistry panel (including liver-function tests), total cholesterol, standard urine testing, and urine pregnancy test for women of child-bearing potential (WOCBP). Blood and urine will be collected from each patient as specified in the Schedule of Visits and Procedures or as clinically indicated. Laboratory samples are to be shipped on the same day as collected. Laboratory test results will be provided to the sites through a web-based reporting system. Alert values will be emailed to the site. Laboratory data will be transferred to the clinical database from the central laboratory database.

Screening laboratory test results must be reviewed by the Investigator prior to patient enrollment. Patients will fail screening for clinically significant laboratory values. However, at the discretion of the Investigator, screening laboratory tests may be repeated one time to confirm out-of-range results or clinical significance. Specific laboratory tests are listed in [Table 2](#).

The central laboratory should be used for all laboratory testing required for a patient during study participation, including laboratory testing needed for unscheduled visits. Clinically significant laboratory results must be entered as a diagnosis on the AE eCRF rather than as an individual test result. Patients with clinically significant laboratory test results will be evaluated, treated and followed at the discretion of the Investigator until the value returns to clinically acceptable levels.

Throughout the study, all laboratory results should be reviewed and signed by the Investigator within 48 hours of receipt of the report (whenever possible).

Table 2 Laboratory Parameters

Hematology	Chemistry	Urine

 • Hematocrit (HCT) • Hemoglobin (HGB) • Red blood cells (RBC) • White blood cells (WBC) • Mean corpuscular hemoglobin (MCH) • MCH concentration (MCHC) • Mean corpuscular volume (MCV) • RBC morphology • Platelet count • Neutrophils • Lymphocytes • Monocytes • Eosinophils • Basophils 
Screening only:
 
 • HIV Antibody (HIV Ab) • Hepatitis B Antibody (HBcAb) Hepatitis B Antigen (HBsAg) • Hepatitis C Antibody (Hep C Ab) 	
 • Sodium • Potassium • Chloride Calcium • Phosphorus • Bicarbonate • Uric Acid • Blood urea nitrogen (BUN) • Creatinine • Total Protein • Albumin • Aspartate aminotransferase (AST) • Alanine aminotransferase (ALT) • Lactic dehydrogenase (LDH) • Gamma-glutamyl transpeptidase (GGT) • Alkaline phosphatase • Bilirubin (total and direct) • Total cholesterol • Non-fasting glucose 
For all female patients (WOCBP) at Screening:
 
 • Serum beta human chorionic gonadotropin (β-hCG) 	
 • pH • Specific gravity, protein • Glucose • Ketones • Bilirubin • Blood • Nitrite • Urobilinogen • Leukocyte esterase 
At all visits except screening (WOCBP only):
 
Urine beta human chorionic gonadotropin (β-hCG)

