6.6 Patient Randomization

All patients will be randomized to study treatment using an IWRS. Study randomization will occur across study sites. After written informed consent has been obtained, all patients will receive a six-digit screening number (XXX-XXX = site number-patient number), assigned in EDC (via iMedidata Rave in sequential order), which will be assigned by the site. Sites should assign the patient numbers in the order that they are screened and enter patients in EDC in the same order. Following completion of the screening period, and after all patient eligibility requirements are confirmed on Day 1 (Baseline), the patient's screening number will be entered in the IWRS, and the patient will be assigned a patient study-drug kit. One kit will provide all the study drug for that patient based on the assigned treatment group.

Patients will be randomized 3:3:3:2 to one of the following treatment groups. The dosing schedule by treatment group is shown in [Table 1](#).

Treatment Group 1: Lebrikizumab, 125 mg every 4 weeks

Baseline: Loading dose of 250 mg (two injections of 1 mL of 125 mg/mL drug product and two injections of 1 mL placebo);

Week 2: Four 1-mL injections of placebo

Weeks 4, 8, 12: 125 mg (one 1-mL injection of 125 mg/mL drug product and one 1-mL injection of placebo)

Week 6, 10, 14: Two 1-mL injections of placebo

Treatment Group 2: Lebrikizumab, 250 mg every 4 weeks

Baseline: Loading dose of 500 mg (four 1-mL injections of 125 mg/mL drug product)

Week 2: Four 1-mL injections of placebo

Weeks 4, 8, 12: 250 mg (two 1-mL injections of 125 mg/mL drug product);

Week 6, 10, 14: Two 1-mL injections of placebo

Treatment Group 3: Lebrikizumab, 250 mg every 2 weeks

Baseline and Week 2: Loading dose of 500 mg (four 1-mL injections of 125 mg/mL drug product)

Week 4, 6, 8, 10, 12, 14: 250 mg (two 1-mL injections of 125 mg/mL drug product)

Treatment Group 4: Placebo every 2 weeks

Baseline and Week 2: Placebo (four 1-mL injections of placebo)

Week 4, 6, 8, 10, 12, 14: Two 1-mL injections of placebo

Table 1 Dosing Schedule by Treatment Group

Group	Baseline	Week 2	Week 4	Week 6	Week 8	Week 10	Week 12	Week 14
1	250 mg	Placebo	125 mg	Placebo	125 mg	Placebo	125 mg	Placebo
2	500 mg	Placebo	250 mg	Placebo	250 mg	Placebo	250 mg	Placebo
3	500 mg	500 mg	250 mg	250 mg	250 mg	250 mg	250 mg	250 mg
4	Placebo	Placebo	Placebo	Placebo	Placebo	Placebo	Placebo	Placebo

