7.1 Screening Visit

The purpose of the screening visit/period is to ensure that appropriate patients are entered into the study and that they remain stable during the pre-treatment period.

- Obtain written informed consent prior to performing any study procedures.
- Review Inclusion/Exclusion Criteria.
- Collect demographic information.
- Complete medical history/review of systems.
- Collect concomitant-medication and procedure/therapy information.
- Perform a complete physical examination, including height and weight.
- Measure vital signs.
- Draw blood samples for laboratory tests, including serum pregnancy test (screening visit only).
- Collect urine sample for urinalysis.
- Complete the following assessments:

- Investigator’s Global Assessment (IGA)
- Eczema Area and Severity Index (EASI)
- Body Surface Area (BSA)
- Instruct the patient to apply an emollient twice daily.
- Schedule next visit.

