7.2 Baseline Visit (Day 1)

- Confirm emollient use.
- Re-assess and confirm patient eligibility (Inclusion/Exclusion criteria).
- Measure weight and vital signs.
- Collect concomitant medication and procedure/therapy information.
- Query for adverse events (AEs) since the last visit.
- Collect a 12-lead ECG.
- Draw blood samples for laboratory tests (hematology and chemistry)
- Draw a pre-dose blood sample for PK and anti-drug antibody (ADA) testing.
- Conduct urine for urinalysis and urine pregnancy test (WOCBP only).
- Dispense electronic tablet that will be used for home recording of pruritus NRS and sleep-loss NRS (daily), and ADIQ (weekly).
- Train patient on the use of the electronic tablet.
- Review compliance report on the electronic tablet for the assessments (pruritus NRS, sleep-loss NRS, and ADIQ) and remind patient to record daily.
- Complete the following assessments:
 - Investigator’s Global Assessment (IGA)
 - Eczema Area and Severity Index (EASI)
 - Body Surface Area (BSA)
 - Patient Oriented Eczema Measure (POEM)
 - Dermatology Life Quality Index (DLQI)
 - Hospital Anxiety and Depression Scale (HADS).
- Randomize the patient.
- Administer study drug.
- Instruct the patient to apply an emollient twice daily.
- Schedule next visit.

7.3 Visits on Day 15, Day 29, Day 43, Day 57, Day 71, Day 85 and Day 99 (+/- 3 Day)

- Confirm emollient use.

- Measure vital signs.
- Collect concomitant-medication information.
- Review and record AEs.
- Review compliance report on the electronic tablet for the daily assessments (pruritus NRS, sleep-loss NRS, and ADIQ) and remind patient to continue daily record.
- At **Day 29, 57, and 85**, draw blood samples for laboratory tests, and collect urine for urinalysis and pregnancy test (WOCBP only).
- At **Day 29, 57, and 85**, complete the following assessments:
 - Investigator’s Global Assessment (IGA)
 - Eczema Area and Severity Index (EASI)
 - Body Surface Area (BSA)
- At **Day 57** complete the following assessments:
 - Dermatology Life-Quality Index (DLQI)
 - Hospital Anxiety and Depression Scale (HADS).
- At **Day 15, 29, 57, and 85**, collect blood samples for PK (see Section 8.2.2 for instructions).
- At **Day 15 and 29**, collect a pre-dose blood sample for ADA testing (see Section 8.2.2 for instructions).
- Administer study drug.
- Remind the patient to apply an emollient twice daily.
- Remind the patient to use the tablet daily.
- Schedule next visit.

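### The Day 1 urine pregnancy test is routed to the central laboratory with no on-site exception, so its result would be expected only after randomization and the first dose

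*Protocol*

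**What the plan says.** Protocol Section 9.1.4 opens by sending laboratory tests to a central laboratory. The same sentence ends its list with "total cholesterol, standard urine testing, and urine pregnancy test for women of child-bearing potential (WOCBP". The section then says "Laboratory samples are to be shipped on the same day as collected", has results returned to sites by a web-based system, and adds that "all laboratory results should be reviewed and signed by the Investigator within 48 hours of receipt of the report", qualified by a note that this applies whenever possible. On scope it says "The central laboratory should be used for all laboratory testing required for a patient during study participation". The one rule tying a result to enrollment is "Screening laboratory test results must be reviewed by the Investigator prior to patient enrollment". Table 2 lists urine β-hCG with the other parameters and has no note about local testing.

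Section 7.1 (Screening) has the line "Draw blood samples for laboratory tests, including serum pregnancy test (screening visit only"; Appendix 1 puts that visit at day -30 to -7. Section 7.2 (Baseline, Day 1) has "Conduct urine for urinalysis and urine pregnancy test (WOCBP only", and later in the same list randomization and study-drug administration. Section 6.6 permits IWRS entry "after all patient eligibility requirements are confirmed on Day 1 (Baseline". Section 5.2 excludes pregnant women and women planning pregnancy (item 16), and sexually active women of reproductive potential who are unwilling to use adequate contraception (item 17).

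**The concern.** A pregnancy test scheduled on the day of first dosing is useful for eligibility only if someone reads it before the injection. As routed, the Day 1 sample leaves the site that day and the result comes back later, while randomization and the loading dose take place at the same visit. A woman who conceived after the Screening serum test, despite the contraception criterion, could be randomized and dosed before her result is seen.

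This is a participant-safety and eligibility point. It does not touch power, the type I error rate or the primary estimate. The sponsor plainly regards exposure in pregnancy as something to avoid: contraception is required until 120 days after the last dose (Section 5.2, item 17), and pregnancy requires stopping study drug (Sections 9.1.8 and 10.3).

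**Working it through.** **Sequence.** The plan states no figure to reproduce, so the first step is to put the relevant text in time order.

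| Step | When | Source |
|---|---|---|
| Serum pregnancy test | Day -30 to -7 | Section 7.1, Appendix 1 |
| Screening results reviewed | Before enrollment | Section 9.1.4 |
| Urine pregnancy test | Day 1 | Section 7.2 |
| Eligibility confirmed, kit assigned | Day 1 | Section 6.6 |
| First injection | Day 1 | Section 7.2 |
| Urine sample shipped | Day 1 | Section 9.1.4 |
| Result returned by web | Turnaround not stated | Section 9.1.4 |

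Nothing in Section 7.2 says the urine result must be read between collection and randomization, and neither document mentions an on-site, dipstick or point-of-care test. Elsewhere the protocol does state an order when it wants one: Day 1 PK and ADA blood is drawn pre-dose (Section 7.2), and the IGA must precede the EASI (Section 8.2.1.1).

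This leaves two readings of Section 6.6.

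- If confirming eligibility needs the Day 1 urine result, the central route does not fit a one-visit Baseline.
- If it does not, pregnancy eligibility rests on a serum result 7 to 30 days old, plus the contraception and planned-pregnancy exclusions.

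**Size under the second reading.** From the protocol: about 275 patients, randomized 3:3:3:2. Groups 2 and 3 receive 500 mg on Day 1; Group 1 receives 250 mg.

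- On active drug: 275 × 9/11 = 225
- Given 500 mg on Day 1: 275 × 6/11 = 150

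The documents give no count of women of child-bearing potential and no pregnancy rate. Assumed: 25-40% of patients are such women, and 0.1-0.7% of them have an undetected pregnancy on Day 1. Annualized over a 30-day window, those rates are 0.001 × 365/30 = 1.2% and 0.007 × 365/30 = 8.5% per year.

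- Women of child-bearing potential on active drug: 225 × 0.25 = 56.25 to 225 × 0.40 = 90
- Expected pregnancies exposed to active drug: 56.25 × 0.001 = 0.06 to 90 × 0.007 = 0.63
- Of these, at 500 mg: 150 × 0.25 × 0.001 = 0.04 to 150 × 0.40 × 0.007 = 0.42
- If an on-site urine test detects only half: 0.03 to 0.32

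Those figures use the longest screening interval. At the shortest, 7 days, the same annual rates give 0.001 × 7/30 = 0.023% to 0.007 × 7/30 = 0.16%, so 56.25 × 0.00023 = 0.01 to 90 × 0.0016 = about 0.15 women on active drug.

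**The case against.** The strongest reply is that the gate already exists. Section 6.6 requires all eligibility to be confirmed on Day 1, Section 7.2 separately requires eligibility to be re-confirmed at Baseline, pregnancy is an exclusion, and the urine test is listed ahead of randomization. On that reading no woman may be dosed before her result is known, and only a logistics mismatch remains. This is a fair reading, and the exposure figures do not arise under it. It does not rescue the text, because a site following both sections literally could not complete Baseline in one visit.

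Several smaller points stand in part:

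- No turnaround time is given, so the lateness of the result is inferred from same-day shipping and web reporting. The 48-hour rule runs from receipt of a report and sets no turnaround.
- The scope sentence in Section 9.1.4 says the central laboratory *should* be used, which is not absolute. The section's opening sentence, however, is unconditional.
- Section 7.2 speaks of conducting the urine tests, whereas Sections 7.3, 7.4 and 7.6 speak of collecting urine. This might hint at on-site testing, but the same verb covers urinalysis, so it is weak evidence.
- Sites may run a dipstick anyway. The protocol does not tell them to, and with about 60 sites practice could differ.
- The mitigations are real: the Screening serum test, the contraception and planned-pregnancy exclusions, repeat urine tests at Days 29, 57 and 85, and withdrawal of study drug on pregnancy. They do not cover a conception during the screening interval before the first dose.

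**Conclusion.** The concern holds as a minor one. The routing of the urine pregnancy test to the central laboratory, with no exception, is on the page. That the Day 1 result arrives after dosing is a well-supported inference, not a stated fact. No text expressly requires a negative Day 1 result.

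The expected number of exposed pregnancies is below one throughout the assumed range: 0.06 to 0.63 for a 30-day interval, and about 0.01 to 0.15 for a 7-day interval. These are upper bounds on what an on-site test would prevent, because urine tests miss very recent conceptions. They depend wholly on the assumed share of women of child-bearing potential and the assumed pregnancy rate. The case for changing the text is that the test is already scheduled and paid for, but as routed it would not be expected to inform the decision it precedes.

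**What to change.** - **Section 9.1.4:** exempt the urine pregnancy test from the central-laboratory wording, with a matching note in Table 2. The Screening serum test stays central.
- **Section 7.2:** state that the urine pregnancy test is read on site and must be negative before IWRS entry and the first dose.
- **Section 7.3 (optional):** state that the test is read on site before dosing at Days 29, 57 and 85. This is a sensible extension; nothing in Section 10.3 is contradicted as it stands.

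The cost is two or three sentences, urine test strips and a few minutes' wait before dosing for the women concerned. No visit or sample is added. Under Section 12.1 the change needs an amendment with IRB/IEC approval, so it is best carried with the next amendment made for other reasons.
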